### ANALYSIS SET AND STUDY POPULATIONS

The primary outcome of the study will be analyzed according to the intention-to-treat (ITT) principle. The full analysis set of data will be derived from the set of all randomized participants. Participants allocated to a treatment group (i.e., ES or CTL) will be analyzed as members of that group irrespective of their compliance to the planned treatment. Those with both missing baseline and follow-up value will not be included in the analysis, which is unbiased under a plausible missing at random assumption. All outliers that are within the realm of biological plausibility will be included in the analysis and only obvious data errors (e.g., resulting from technical issues) will be excluded. If there are statistical outliers within the realm of biological plausibility ( $>2.2^*IQR$ ), the data will be explored with and without the outliers included for completeness.

## ANALYSIS OBJECTIVES, OUTCOMES, AND STATISTICAL METHODS

All data will be collected longitudinally. Statistical analysis will be performed blinded to participant allocation after the last participant has completed the trial. Descriptive statistics will be summarized as mean (SD) for continuous and N (%) for categorical data, and data will be assessed for skewness and normality using Q-Q plots and Shapiro-Wilk tests (non-normal distributions will be log transformed as needed).

### Outcomes

| Category                                       | Variable   | Timepoints                    |
|--|--|-------------------------------|
| Anthropomorphic Measures                       | Weight, Waist circumference, body mass index (BMI)   | Baseline, 12 weeks            |
| Blood Pressure                                 | Systolic, Diastolic, Mean Arterial Pressure  | Baseline, 12 weeks            |
| Blood Biochemistry                             | Fasting plasma insulin, fasting plasma glucose, HOMA-IR, fasting plasma cytokines  | Baseline, 12 weeks            |
| Complete Blood Count                           | Total White Blood Cells, Hematocrit, Hemoglobin, Monocytes, Neutrophils  | Baseline, 12 weeks            |
| Exercise Behavior (GLTEQ)                      | Bouts of mild, moderate, and strenuous exercise lasting >15min, weekly leisure-time exercise   | Baseline, 12 weeks            |
| Cardiorespiratory Fitness                      | Cycling? VO 2 peak, max HR, peak RER, peak power output (W)   | Baseline, 12 weeks            |
| Movement Break Adherence (Device-worn)         | Device wear time, average minutes per day of total, light, moderate, vigorous, and moderate-vigorous physical activity per day, average minutes of sedentary time per date, sit-to-stand ratio per day | Baseline, week 2 and, week 11 |
| Movement Break Adherence (Self-report)         | Weekly surveys assessing number of movement breaks completed   | Weekly for 12 weeks           |
| Movement Break Adherence (technology platform) | Number of movement breaks completed within the Seven Movements account   | Recorded for each snack       |
| EES  | Exercise enjoyment
1 (Not at all)
2 (Very light)
3 (Slightly)
4 (Moderately)
5 (Quite a bit)
6 (Very much)
7 (Extremely)  | Following each snack          |
| Borg CR-10 scale                               | Rating of perceived exertion
0 (Rest)
1 (Very, very easy)
2 (Easy)
3 (Moderate)
4 (Somewhat hard)
5 (Hard)
6
7 (Very hard)   | Following each snack          |

|  |                        |  |
|--|------------------------|--|
|  | 8
9
10 (Maximal) |  |
|--|------------------------|--|

**Primary outcome:** The prespecified primary outcome for this trial will be a comparison of the change in VO2peak (mL/kg/min) from baseline to 12 weeks between the movement break intervention groups.

The primary data analyses will be intention-to-treat. Data will be analyzed by constrained longitudinal data analysis (cLDA) via a linear mixed model with fixed effects for timepoint (i.e., baseline and week 12), the interaction between timepoint and intervention group (i.e., ES or CTL), and stratified allocation factors (sex, study site) as well as random effects for participants to account for the correlation of repeated measures within participants. The between-group treatment (interaction) effect estimate at 12 weeks with 95% confidence intervals will be reported as the main analyses of interest. Significance will be set at  $p<0.05$  and Cohen's d effect sizes will be calculated to estimate the magnitude of between-group differences in pre-post change scores.

The cLDA approach constrains the baseline means to be equal between the treatment groups, which is a reasonable assumption in the context of a randomized clinical trial. No missing data will be imputed as per contemporary guidelines [3]. Model specification will be assessed visually using normal probability plots and residuals vs. fitted values plots. Models will be run using log-transformed outcome variables when departure from model assumptions is observed.

**Secondary outcome measures:** To supplement the primary outcome of VO2peak in mL/kg/min we will also analyze peak power output and absolute VO2peak (L/min). Key secondary outcomes will include exercise adherence, enjoyment, and perceived exertion assessed by self-report. Self-reported adherence to the intervention will be determined by user analytics on the Seven Movements platform and using the automated weekly REDCap surveys. We will define high, moderate, or low adherence as completing >67%, 50-66% or <50% of the prescribed intervention (i.e., total # of snacks performed relative to minimum prescription of 9 snacks per week and the number of days when participants completed  $\geq 3$  snacks relative to a prescription of 3 days per week). Enjoyment (Exercise Enjoyment Scale) and perceived exertion (Borg CR-10 scale) will be asked following each snack. Adherence, enjoyment, and exertion data will be analyzed using a linear mixed model that will include fixed effects for group (ES vs. CTL), timepoint (week, Phase or session number), their interaction, and stratified allocation factors (site, sex) and random effects for participants. In these analyses, the main effect of group will be most important to identify an overall effect of the intervention on these variables.

Other continuous secondary outcomes assessed at baseline and a follow-up timepoint will be analyzed similarly to the primary outcome using a constrained baseline longitudinal data analysis linear mixed model (with all relevant follow-up timepoints included as a fixed factor of time in the model). Secondary outcomes include:

- Changes in anthropometrics assessed at baseline and 12-weeks.
- Changes in blood markers (fasting plasma glucose, insulin, HOMA-IR, inflammatory cytokines) assessed at baseline and 12 weeks.

- Changes in hematology analysis of complete blood count (total white blood cells, hematocrit, hemoglobin, monocytes, neutrophils) assessed at baseline and 12-weeks.
- Changes in device-worn physical activity and sedentary time assessed at baseline, week 2, and week 11 via device-worn measurement.
- Changes in leisure time physical activity assessed by GLTEQ measured at baseline and 12 weeks.

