### *Study Design*

We will conduct a two-centre proof-of-concept parallel arm randomized trial where participants will be randomized (1:1 allocation ratio stratified by sex and centre) into an Exercise Snacks or Placebo Exercise Control group for 12 weeks. Interventions will be delivered at home or work via the functioning Seven Movements platform ([www.sevenmovements.com](http://www.sevenmovements.com)) and individualized via onboarding sessions to develop an action plan for incorporating exercise

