### A PRIORI SAMPLE SIZE CONSIDERATIONS

A sample size of 30 participants per group was deemed sufficient to detect a within-between interaction with a medium effect size (Cohen's  $f=0.25$ ,  $d=0.50$ ) for the primary outcome (CRF) assuming 90% power with a two-tailed  $\alpha$  set at 0.05 (G\*Power v3.1). This effect size equates to ~1 metabolic equivalent (MET) increase in CRF (assuming a mean baseline VO2peak of 30-35 mL/kg/min with a SD of 5-7 mL/kg/min[4-9]). The grant was funded by the Canadian Cancer Society Action Grant special call for interventions designed for primary cancer prevention. A 1-MET increase in CRF was deemed clinically relevant for primary cancer prevention based on epidemiological data showing 10-21% decrease in cancer incidence for each 1 MET increase in CRF[1-2]. To preserve power and account for a 20-30% dropout rate, we aimed to recruit 40 participants per group (80 participants total; equal sex distribution). Randomization was stratified based on study site (i.e., Mac or UBC) and participant sex (i.e., male or female). These calculations were documented in the original grant application (Feb 2021), trial protocol (Oct 6, 2022), and SAP (V1 June 2023).

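### The primary mixed model adjusts for sex and site as level shifts only, so it assumes equal 12-week change across the randomisation strata; adding stratum-by-timepoint terms is a cheap improvement

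*SAP*

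**What the plan says.** The SAP (Outcomes) defines the primary outcome as a "comparison of the change in VO2peak (mL/kg/min) from baseline to 12 weeks between the movement break intervention groups". The fixed effects are timepoint, timepoint-by-group and the strata, described as "stratified allocation factors (sex, study site) as well as random effects for participants". There is no main effect of group, because the method "constrains the baseline means to be equal between the treatment groups". The reported result is the week-12 contrast: "The between-group treatment (interaction) effect estimate at 12 weeks with 95% confidence intervals will be reported as the main analyses of interest".

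The strata are those used for allocation. The SAP (A Priori Sample Size Considerations) states: "Randomization was stratified based on study site (i.e., Mac or UBC) and participant sex". The protocol (Study Design) agrees: "1:1 allocation ratio stratified by sex and centre".

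On missing data, the SAP (Analysis Set and Study Populations) relies on missing at random. Its section on handling of missing data declines imputation of the outcome measures for the primary analysis and keeps participants with either visit. The sample-size section allows for 20 to 30% dropout. The remaining secondary outcomes measured at baseline and follow-up use the same kind of model.

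No sex-by-timepoint or site-by-timepoint term is listed. The sentence could be stretched to attach the strata to the timepoint interaction, but the plain reading is main effects.

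**The concern.** A main effect of site moves both visits at that laboratory by the same amount. It cannot represent a different 12-week change at the two laboratories, and the same holds for sex. The plan therefore assumes equal change across strata without saying so.

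Two things follow if the assumption fails. First, the between-stratum spread in change stays in the residual, so the standard error is too large. Second, the claim that the model handles missing outcomes under missing at random needs a correct week-12 mean given the observed predictors of dropout. Loss that depends on arm and site is missing at random, yet a model that forces equal change across sites can still give a biased treatment estimate. The stake is modest extra width in the primary confidence interval and, under a specific dropout pattern, a small bias in the primary estimate.

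**Working it through.** **Inputs from the documents.** SD of VO2peak 5 to 7 mL/kg/min; 30 per group needed; 80 recruited; 20 to 30% dropout. The target is reproduced by 60/(1 − 0.25) = 80, or 40 per arm. No figure in the plan bears directly on the stratum terms.

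**Assumptions not in the documents.** SD 6 (mid-range), correlation between visits 0.85 unless stated, sex gap in level 6 mL/kg/min, true effect 1.75 mL/kg/min, a stratum difference in change Δ of 0 to 3 mL/kg/min, and the retention patterns below.

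**Step 1: what the planned main effects do.** With the baseline constraint, the treatment contrast is the week-12 difference minus b times the baseline difference, where b is the slope of week 12 on baseline. Without a sex term, a unit sex shift leaves (1 − b) × imbalance in the contrast. For 20/30 v 15/30 men the imbalance is 0.167, which leaves 0.083, 0.050, 0.033 and 0.017 at b = 0.5, 0.7, 0.8 and 0.9. With the sex main effect it is 0.

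Under unbalanced dropout the main effects matter more. With 10% v 40% loss by sex and arm, and no difference in change, simulated bias falls from −0.22 to +0.02 at correlation 0.8 and from −0.55 to −0.06 at 0.6. (These runs used a site gap of 1 and a true effect of 2.5; simulation error is about 0.04 to 0.05.)

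**Step 2: standard error when change differs by site.** Take complete data, n = 32 per arm (40 × 0.80) and equal sites. The planned model fits a constant site effect of Δ/2. It therefore misses each site mean by Δ/4, in opposite directions at the two visits. The pooled variance becomes V = 36 + Δ²/16 and the covariance C = 0.85 × 36 − Δ²/16 = 30.6 − Δ²/16. The reported SE is √[(2/n)(V − C²/V)].

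| Δ | V − C²/V | SE | Excess over Δ = 0 |
|---|---|---|---|
| 0 | 9.99 | 0.79 | – |
| 1 | 10.20 | 0.80 | 1.1% |
| 2 | 10.84 | 0.82 | 4.2% |
| 3 | 11.89 | 0.86 | 9.1% |

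Simulation of the planned model gives the same mean SEs: 0.80, 0.82 and 0.86, against a true spread of 0.78 to 0.80 (about 2%, 3% and 9% too large). With even 75% retention and Δ = 2, the mean SE is 0.85 as planned v 0.82 with the extra terms (0.85/0.82 = 1.04). In the complete-data runs, power at Δ = 2 and 3 is 54% and 50% as planned, v 57% and 58% with the terms.

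**Step 3: bias when loss differs by arm within site.** Assume retention by site of 85%/70% in control and 65%/80% in exercise snacks, which averages 75%. The second site's share of completers is 70/155 = 0.452 in control and 80/145 = 0.552 in exercise snacks, a gap of 0.10. If change is larger by Δ at that site, the bias is about 0.10 × Δ.

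| Δ | 0.10 × Δ | Simulated, as planned | Simulated, with stratum-by-time terms |
|---|---|---|---|
| 1 | 0.10 | 0.08 to 0.14 | 0.04 or less |
| 2 | 0.20 | 0.19 to 0.21 | 0.02 or less |
| 3 | 0.30 | 0.27 to 0.30 | 0.02 or less |

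The ranges are across independent simulations. For sex, with retention 90%/60% v 60%/90%, the shares are 0.60 and 0.40. A difference in change of 1 then gives about 0.20. Simulation gives 0.17 to 0.20 in absolute size as planned and 0.02 or less with the terms.

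**Step 4: cost when change does not differ.** Mean SE with the extra terms v as planned is 0.813 v 0.809 with even dropout (0.5%) and 0.838 v 0.816 with strongly unbalanced dropout (2.7%).

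**The case against.** The strongest case against is that the plan already adjusts for both randomisation factors and that the adjustment works. Step 1 bears this out. A reader might infer that, because the outcome is a change, the strata cancel from the contrast and the adjustment is empty. Exact cancellation belongs to a model with a free group difference at baseline and complete data; it does not hold for the constrained model in the SAP. A reader might also infer that the model cannot deal with uneven loss across strata. That is not so either: where strata differ in level but not in change, the planned main effects remove nearly all of the bias.

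It is also fair that harm needs a stratum difference in change, and that bias needs arm-by-stratum loss as well. Nothing in the documents indicates drift at either laboratory. The protocol describes one exercise test and one metabolic-cart model, and requires the same testing order and procedures at both visits. A site difference of 3 is extreme, being close to the protocol's 3.5 mL/kg/min for 1 MET. The standard-error effect is conservative, and the extra terms are not entirely free.

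What survives is that equal change across strata is assumed but not stated, while the missing-data argument depends on it when dropout varies by arm and stratum. The protocol's plan to explore a sex-by-treatment interaction concerns a different term, so it neither supports nor replaces the terms proposed here.

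**Conclusion.** The point holds as a low-cost improvement. Main effects of sex and site handle level differences, including under unbalanced dropout, but impose equal 12-week change across strata. For an assumed site difference in change of 1 to 2 mL/kg/min, the standard error is about 1 to 4% too large, and about 9% at 3. If loss also differs by arm within site as in Step 3, the bias is about 0.1 to 0.2 mL/kg/min. Against the SAP's target of about 1 MET (3.5 mL/kg/min), that is 0.1/3.5 = 3% to 0.2/3.5 = 6%; against a standard error of 0.82 it is 12 to 24%.

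These sizes rest on the assumed correlation, stratum differences and retention pattern. With no stratum difference in change there is nothing material to gain. The documents do not support reading this as a demonstrated bias or as a failure to adjust for the strata.

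**What to change.** In the SAP's primary model, list the fixed effects as timepoint, timepoint-by-group, sex, site, sex-by-timepoint and site-by-timepoint. This also settles how the present sentence should be read. The treatment effect stays common to all strata; these are not treatment-by-stratum terms. Make the same change in the secondary models that use the constrained-baseline approach. For device outcomes with two follow-ups, each factor needs one term per follow-up, so four parameters and not two.

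The SAP says the trial was completed in December 2023 and that analysis is blinded to allocation. If the data are still blinded, amend the primary model. If they are unblinded, keep the primary model as written and report the extended one as a labelled sensitivity analysis. No new data are needed. The cost is two parameters in the primary model and, when change does not differ by stratum, the increase in standard error shown in Step 4.

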## HANDLING OF MISSING DATA AND OTHER DATA CONVENTIONS

No statistical imputations will replace missing data for the outcome measures (data as observed). However, the constrained baseline longitudinal data analysis – in a linear mixed model with restricted maximum likelihood – is a principled approach to addressing missing outcome data, including the baseline value of the continuous outcome measure. The model permits the inclusion of all participants in the analysis with either a baseline or a follow-up value. Thus, missing data will not be imputed for the ITT analyses. If a blood marker value is below the detection limit, we will explore the results following imputation of the value as limit of detection (LOD) divided by the square root of 2 (6).

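### The primary mixed model states no covariance structure, and its natural reading (random intercept, one residual variance) gives wrong standard errors if the spread of VO2peak changes by week 12

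*SAP*

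**What the plan says.** The SAP's primary-outcome text (under Outcomes) sets out a constrained longitudinal model with "fixed effects for timepoint (i.e., baseline and week 12"), the time-by-group interaction, sex and site. The random part is "random effects for participants to account for the correlation of repeated measures within participants". On the constraint it says: "The cLDA approach constrains the baseline means to be equal between the treatment groups". The section on missing data adds that estimation is "in a linear mixed model with restricted maximum likelihood".

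No covariance structure, visit-specific residual variance, robust standard error or degrees-of-freedom method is named. The protocol's Statistical Analysis section, which lists participant and site as random effects, names none either.

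The planned check is "Model specification will be assessed visually using normal probability plots and residuals vs. fitted values plots". The only remedy is "Models will be run using log-transformed outcome variables when departure from model assumptions is observed".

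Under Secondary outcome measures, other continuous outcomes get a similar model, "with all relevant follow-up timepoints included as a fixed factor of time in the model". This includes the accelerometer outcomes at baseline, week 2 and week 11.

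**The concern.** With two measurements per person, a random slope in time cannot be separated from the residual. The model that the text most naturally describes is therefore a random intercept plus a single residual variance, that is, compound symmetry, with the same SD at both visits.

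In a constrained-baseline model, this matrix fixes both the weight given to the baseline value and the standard error of the week-12 effect. If the true SD at week 12 differs from baseline, the weight is not the regression slope and the reported standard error is not the true one. Intervals are too narrow when the spread grows and too wide when it shrinks. Some change is reasonable to plan for: prescriptions are individualised and progressed, and the protocol expects adherence to fall over the intervention, so responses may vary between people.

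At stake are the p-value and confidence interval of the primary outcome. The text also allows different analysts to fit models that give different p-values from the same data.

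**Working it through.** **Inputs.** From the SAP: two visits for the primary outcome; baseline SD 5-7 mL/kg/min; 30 evaluable and 40 recruited per group; 20-30% dropout; two-sided alpha 0.05. From the protocol: 1:1 allocation. Not in the documents, so assumed: the ratio r of week-12 to baseline SD (0.8 to 1.3) and the pre-post correlation.

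**The plan's own figure.** The sample-size statement ("A sample size of 30 participants per group was deemed sufficient to detect a within-between interaction") does not reveal the assumed covariance. The G*Power formula is λ = N·f²·m/(1−ρ), with m = 2 and f = 0.25. At ρ = 0.5 and N = 60, λ = 60 × 0.0625 × 2 / 0.5 = 15 and power is 96.8%; 46 in total would suffice for 90%. A total of 60 corresponds to 90% power at a correlation of about 0.31-0.32, which the SAP does not state. So 30 per group is not reproduced from the stated inputs alone, and it cannot be used to infer the intended structure.

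**Two visits, complete data, equal arms.** Set the baseline variance to 1. Let v be the week-12 variance averaged over arms and c the averaged covariance. Compound symmetry fits a common variance s = (1+v)/2 and a baseline weight b = c/s.
- Model variance of the effect, up to a common factor: s(1−b²) = (s²−c²)/s.
- True variance: v + b² − 2bc = v(s²−c²)/s², using 1 − 2s = −v.
- Model/true = s/v = (1+v)/(2v).

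The correlation cancels, so only the SD ratio matters. If both arms change, v = r². If only ES changes, v = (1+r²)/2. True alpha = 2[1 − Φ(1.96·√((1+v)/(2v)))].

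| r | Arms changing | v | Model SE / true SE | True alpha |
|---|---|---|---|---|
| 0.8 | ES only | 0.820 | 1.053 | 3.9% |
| 0.8 | both | 0.640 | 1.132 | 2.7% |
| 1.0 | none | 1.000 | 1.000 | 5.0% |
| 1.1 | ES only | 1.105 | 0.976 | 5.6% |
| 1.1 | both | 1.210 | 0.956 | 6.1% |
| 1.2 | ES only | 1.220 | 0.954 | 6.2% |
| 1.2 | both | 1.440 | 0.920 | 7.1% |
| 1.3 | ES only | 1.345 | 0.934 | 6.7% |
| 1.3 | both | 1.690 | 0.892 | 8.0% |

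A common unstructured 2x2 matrix has model SE equal to true SE in all these balanced cases.

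**Simulation.** REML, 40 per arm, SD 6, 25% completely random dropout, 4,000 runs per scenario (Monte Carlo error near 5%: √(0.05 × 0.95 / 4000) ≈ 0.3 points). At correlation 0.7, type I error for random intercept versus unstructured was:
- equal SDs: 4.8% vs 5.4%
- +20%, both arms: 7.1% vs 5.2%
- +30%, both arms: 8.3% vs 5.1%
- +20%, ES only: 6.8% vs 6.1%
- +30%, ES only: 6.6% vs 5.2%
- −20%, both arms: 3.2% vs 5.9%

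Mean estimates showed no bias under either model. Power for a 3 mL/kg/min effect with equal SDs was 76.6% vs 77.0%.

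**Three visits, equal SDs.** Assume correlations of 0.7 (baseline-week 2), 0.5 (baseline-week 11) and 0.6 (week 2-week 11). Compound symmetry fits their mean, (0.7+0.5+0.6)/3 = 0.6, so the model variance is 1 − 0.36 = 0.64 at both follow-ups.
- Week 2: true variance 1 + 0.36 − 2(0.6)(0.7) = 0.52; √(0.64/0.52) = 1.109; alpha 3.0%.
- Week 11: true variance 1 + 0.36 − 2(0.6)(0.5) = 0.76; √(0.64/0.76) = 0.918; alpha 7.2%.

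No change in spread is needed here, only correlation that weakens with time.

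**The case against.** **The random intercept is an inference.** The SAP never uses the word intercept, and it says only that secondary outcomes are handled in a similar way. This stands. A reader might infer that the plan commits to a wrong structure; the documents support only that the structure is unstated and that its natural reading is restrictive.

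**The larger figures are stress cases.** This largely stands. The control is designed not to raise fitness, so growth in the ES arm alone is the more natural scenario. A gain of 3.5 mL/kg/min proportional to a baseline of 30-35 gives r = 1 + 3.5/35 = 1.10 to 1 + 3.5/30 = 1.12, hence alpha near 5.6-5.7%. If responses are independent of baseline, ratios of 1.2 and 1.3 at SD 6 need response SDs of 6√0.44 = 4.0 and 6√0.69 = 5.0 mL/kg/min, more than the 1-MET target itself.

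**If nobody responds, the cause of the growth is absent.** True, but the same error affects interval coverage when the mean effect is not zero.

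**The residual checks and log transformation may help.** In part: they address variance that rises with the mean. They do not address variance that differs by visit in general. The per-protocol sensitivity analysis concerns adherence.

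**An unstructured matrix is not a complete or free cure.** This stands. One common matrix does not model a change in ES alone: at r = 1.3 with 28 ES and 32 control completers, its SE is still about 2% too small. Without a small-sample correction, its simulated type I error ran from 4.8% to 6.1% and exceeded 5% in 15 of 16 null scenarios.

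**Conclusion.** The point holds as a gap in specification with a conditional consequence. If the model is fitted as the text most naturally reads, the primary standard error is correct only when the week-12 variance, averaged over arms, equals the baseline variance. For an SD increase of 10-30%, the SE is about 2-7% too small if only ES changes and 4-11% too small if both arms change. If the SD falls, the test is conservative.

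The SD ratios and the three-visit correlations are assumptions; the documents neither show nor rule out a change in spread. The closed-form results assume complete data and equal arms.

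A reader might infer that the treatment estimate is biased. Nothing here shows that: the simulations found no bias, though dropout in them was unrelated to the data and other dropout patterns were not examined. Nor do the documents support saying that the trial's type I error is 7-8%; those values need a 20-30% SD increase in both arms. The change is worth making because it is cheap and because the present wording leaves the primary p-value open to the analyst's choice of structure.

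**What to change.** In the primary-outcome text, replace the random-effects phrase with: REML with an unstructured within-participant covariance (2x2 for baseline and week 12; 3x3 for the accelerometer outcomes) and Kenward-Roger degrees of freedom. State that this applies to all constrained-baseline models.

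Add a sensitivity analysis of the primary outcome with arm-specific covariance matrices or robust standard errors, to cover a change in ES alone with unequal numbers of completers. Report the SD by arm and visit. Record the change before the analyst learns the allocation.

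The cost is a line or two of text and code. The two-visit model goes from two covariance parameters to three; the three-visit model goes from two to six. Simulated power was unaffected. The small-sample correction should not be left out, given the slightly raised type I error seen without it.
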